### NON-SERIOUS, DEVICE-RELATED EVENTS:

For events that are not considered serious but are believed related to the study device (ADEs):

1. Complete a Detailed Adverse Event Form
2. Ensure the data are submitted to AMO electronically within a timely manner.

1 INTRODUCTION

This document summarizes the statistical methods and tables to be implemented during the analysis of data for this feasibility study of a new treatment algorithm (iDesign 1.3-PRESBY) to increase depth of focus after wavefront-guided LASIK correction of myopic refractive errors. This study will be a 9-month, prospective, multi-center, non-randomized, contralateral clinical trial.

All endpoints will be evaluated at 6 months. The primary endpoint is monocular distance corrected intermediate visual acuity (DCIVA). The secondary endpoint is monocular distance corrected near visual acuity (DCNVA). The safety endpoints include monocular best corrected visual acuity (BSCVA), rates of induced manifest astigmatism and rates of serious and device-related adverse event rates.

Other endpoints include monocular and binocular UCDVA and BSCVA, monocular and binocular UCIVA and UCNVA, binocular DCIVA and DCNVA, monocular low contrast BSCVA, monocular mesopic DCNVA, monocular depth of focus, iDesign aberrometry measurements, pupil size, manifest refraction, keratometry, anterior segment evaluation, ocular and visual symptoms.

Table listings are included in Appendix I.

2 ANALYSIS POPULATIONS AND VISIT SCHEDULE

2.1 ANALYSIS POPULATIONS

The safety population will be the primary analysis population for all endpoints and will consist of all eyes that receive study treatment.

2.2 VISIT SCHEDULE

All eyes will be examined preoperatively and at 1 day, 1 week, 1 month, 3 months, 6 months and 9 months. The exact number of days for each interval is described in the protocol. The number of eyes with missing visits or data outside of the visit intervals will be reported.

2.3 DATA CONVENTIONS

Descriptive statistics will typically include sample size (N), mean, standard deviation (SD), median, minimum (Min.), and maximum (Max.) as appropriate for continuous variables. For categorical data, the frequency and proportion will be computed.

Unless otherwise indicated, alpha will be set to 0.05 for two-sided statistical testing.

For visual acuity data, letter scores will be converted to LogMAR values prior to analysis. In addition, if the test distance used is not the standard test distance for the chart, then visual acuity data will be adjusted for the actual test distance used. Appendix II provides formulas for LogMAR conversion and distance adjustment.

For refractive data, all values will be converted to minus cylinder format and sphere will be adjusted for optical infinity. Formulas used for refractive data conversions are included in Appendix III.

3 STATISTICAL METHODS

3.1 ACCOUNTABILITY

Subject accountability will be summarized as a frequency distribution by scheduled visits. The frequency and proportion of available eyes, including those outside of the interval, and the frequency and proportion of missing eyes (forms not yet received, active, missed visit, lost to follow-up or discontinued) will be reported.

3.2 DEMOGRAPHICS

Subject demographic data will be subject-based. Age will be summarized with descriptive statistics with mean, standard deviation, minimum and maximum. The frequency distributions of sex, race, and contact lens history will also be tabulated. The demographic data will also be reported by site.

3.3 PRIMARY ENDPOINT

MONOCULAR DISTANCE CORRECTED INTERMEDIATE VISUAL ACUITY (DCIVA)

The primary endpoint is mean monocular DCIVA under photopic conditions at 67 cm. Results will be reported by CustomVue combined with iDesign 1.3-PRESBY treatments (test) group versusCustomVue (control) group and compared using a one-sided, paired t-test with alpha level of 0.025. The null hypothesis is that the mean difference between eyes (control minus test) for LogMAR DCIVA is less than or equal to zero (ie, test acuity is the same as or worse than that of control). The alternative hypothesis is that the mean difference between eyes for DCIVA is greater than zero (ie, test acuity is better than that of control).

 $H_o: \mu_{diff} \le 0$ (test is worse than (higher LogMAR) or equal to control)

H₁: $\mu_{diff} > 0$ (test is better (lower LogMAR) than control)

where

 μ_{diff} = the mean difference in LogMAR DCIVA between control eyes and test eyes (control minus test)

```
10NOV2015/F
```

Reject the null hypothesis if one-sided p-value ≤ 0.025 .

The success criterion is a statistically significantly lower mean DCIVA for test compared to control ($p \le 0.025$).

In addition, clinical significance will be achieved if the mean DCIVA for the test group is at least one line better than that for the control group.

3.4 SECONDARY ENDPOINT

MONOCULAR DISTANCE CORRECTED NEAR VISUAL ACUITY (DCNVA)

Mean monocular DCNVA at 40 cm will be reported by CustomVue combined with iDesign 1.3-PRESBY treatments (test) group versus CustomVue treatments (control) group and compared using a one-sided, paired t-test with an alpha level of 0.025. The null hypothesis is that the mean difference between eyes (control minus test) for logMAR DCNVA is less than or equal to zero. The alternative hypothesis is that the mean difference between eyes for DCNVA is greater than zero.

 $H_o: \mu_{diff} \leq 0$ (test is worse than (higher logMAR) or equal to control)

H₁: $\mu_{diff} > 0$ (test is better (lower logMAR) than control)

where

 μ_{diff} = the mean difference in logMAR DCNVA between control eyes and test eyes (control minus test)

Reject the null hypothesis if one-sided p-value ≤ 0.025 .

The success criterion is a statistically significantly lower mean logMAR value for test compared to control eyes ($p \le 0.025$).

Clinical significance is achieved if the mean DCNVA for the test group is at least 1.5 lines better than that for the control group.

3.5 SAFETY ENDPOINTS

1. MONOCULAR BSCVA

Mean monocular BSCVA will be reported by test and control groups with the mean difference between postoperative and preoperative BSCVA evaluated using a two-sided, 90% confidence interval (CI). The null hypothesis is that the mean difference (postoperative minus preoperative) in logMAR BSCVA is greater than or equal to 0.1 logMAR. The alternative hypothesis is that the mean difference in BSCVA is less than 0.1 logMAR.

```
  H_{o}: \mu_{diff} \ge 0.1   H_{1}: \mu_{diff} < 0.1  where
```

10NOV2015/F

μ_{diff} = the mean difference in logMAR BSCVA between postoperative and preoperative eyes (postoperative minus preoperative).

The success criterion is achieved if the upper limit of the 90% CI of the differences in mean logMAR BSCVA for postoperative compared to preoperative eyes is < 0.1 logMAR for both test and control groups.

Clinical significance is achieved if the mean postoperative BSCVA is no more than one line worse than preoperative BSCVA for both test and control groups.

2. INDUCED MANIFEST REFRACTIVE ASTIGMATISM

The frequency and proportion of eyes with induced manifest refractive astigmatism will be reported at each periodic study visit. The rate of eyes with induced manifest refractive astigmatism of greater than 2.00 diopters will be summarized.

3. SERIOUS AND DEVICE RELATED ADVERSE EVENTS

The number and proportion of eyes with serious and device-related adverse events (non-flap related) will be summarized.

3.6 ADDITIONAL ENDPOINTS

Summary statistics (mean, standard deviation, median, minimum and maximum) will be reported over time for MRSE.

The frequency, proportion and 95% confidence intervals of eyes with achieved MRSE within 0.50 D and 1.00 D of intended will be summarized over time. The intended MRSE is defined as " – Preop MRSE". The achieved MRSE is defined as "Postop MRSE - Preop MRSE".

Refractive stability will be evaluated for a consistent cohort (i.e., eyes with data at all periodic study visits). At the point of refractive stability, at least 95% of the eyes in the consistent cohort should have a change ≤1.00 D of MRSE between refractions performed at 1 month and 3 months after surgery or any two refractions performed at least 3 months apart. The mean change (paired differences) in MRSE between pairs of successive refractions will be calculated. The 95% confidence intervals of the mean changes should include zero.

The depth of focus curve data will be presented graphically with mean visual acuity on the vertical axis and defocus points on the horizontal axis for test and control groups. The descriptive statistics of defocus for test and control groups will be reported and compared.

Other visual acuity endpoints (such as UCDVA, UCIVA, UCNVA, DCIVA, DCNVA and low contrast BSCVA) will also be reported by test versus control group with the mean difference between groups also determined.

The mean and standard deviation of iDesign aberrometry measurements (HOA) and keratometry (mean and K cylinder) will be reported over time between test and control gorups.

Manifest cylinder will be analyzed as both non-vector and vector variables (Eydelman, et al, 2006). Non-vector analysis includes the descriptive statistics (mean, SD, minimum and maximum) of MRC over time between test and control groups and the accuracy of MRC will also be summarized over time. Vector analysis summary will be reported by test and control group. The mean and standard deviation of intended refractive change (|IRC|), surgically induced refractive change (|SIRC|), error vector (|EV|), correction ratio (CR) and error ratio (ER) will be presented by preoperative MRC categories (>0.50 D to $\leq 1.00 \text{ D}$, >1.00 D to \leq to 2.00 D, >2.00 D to \leq to 3.00 D, >3.00 D to \leq 4.00 D).

Summary statistics (mean, standard deviation, median, minimum and maximum) will be reported over time for pupil size between test and control groups.

The frequency and proportion of eyes with complications and slit-lamp findings, including corneal clarity, will also be reported over time.

The frequency and proportion of responses to each item from the PRVSQ for PRK/LASIK will be analyzed to compare differences between the test and control groups.

The frequency and proportion of eyes with reported ocular visual symptoms (nondirected) will be presented.

A listing of all serious and/or device-related adverse events will also be provided. Additionally, non-refractive retreatment procedures will be tabulated and summarized.

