## STUDY POPULATION CHARACTERISTICS:

**Condition:** Stable myopic refractive error with and without astigmatism and presbyopia.

**Number of Subjects:** Up to 70 subjects will be enrolled to achieve up to 34 treated subjects. Both eyes of subjects will be treated in the study. The control eye will receive the iDesign CustomVue treatment, test eye will receive the PresbyT-LASIK.

Each site should enroll a minimum of 10 subjects.

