## **4. STUDY DESIGN**

This study is a 9 month, prospective, multicenter, non-randomized, contralateral, open-label clinical study.

The study will be conducted at up to 4 sites in Canada and will include up to 34 test group treated eyes (of up to 34 subjects). Subjects must have both eyes treated in the study. The dominant eye will be treated with the control product; the non-dominant eye will be treated with test product. Analyses will be conducted at 6 months.

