### PERIODIC POSTOPERATIVE EXAMINATION PROCEDURES

Periodic examinations will be conducted at 1, 3, 6, and 9 months after treatment. In the event that extended follow-up is not needed, the follow-up period may be reduced.

Note: Subjects are not to wear contact lenses postoperatively until after completion of this study. Wearing contact lenses may potentially cause corneal edema or topography

changes that may influence the visual acuity results. During the study, if correction is required, spectacles should be prescribed.

The following data shall be assessed and recorded for both eyes during the periodic examinations, although not all are required at all periodic visits (see also **Appendix A**). General descriptions and requirements of the various tests are provided in **Appendix C**.

- Ocular and systemic medical history and concomitant medications
- PRVSQ Questionnaire (1, 3, 6, and 9 month visit)
- iDesign System Measurement (refraction, aberrometry, topography, keratometry, pupillometry)
- UCDVA, photopic, monocular
- UCDVA, photopic, binocular
- Manifest Refraction (logMAR)
- BSCVA, photopic, monocular, distance (logMAR)
  - At 3 months or later, if there is a loss of 2 or more lines of BSCVA ( $\geq 10$  letters) compared to the preoperative visit, a rigid contact lens over refraction should be performed to estimate the best possible corrected visual acuity. If a rigid contact lens over refraction is not medically advisable, then a pin-hole acuity should be obtained
- BSCVA, photopic, binocular, distance (logMAR) (3, 6, and 9 month visit)
- BSCVA, photopic, monocular, distance low contrast, 10%, (logMAR) (3, 6, and 9 month visit)
- DCNVA, mesopic, monocular at 40 cm (3, 6, and 9 month visit)
- Pupil size
  - Mesopic, distance and near (3 month visit)
  - Photopic, distance and near (3 month visit)
- DCIVA, photopic, monocular (3, 6, and 9 month visit)
- DCIVA, photopic, binocular (3, 6, and 9 month visit)
- DCNVA, photopic, monocular (3, 6, and 9 month visit)
- DCNVA, photopic, binocular (3, 6, and 9 month visit)
- UCIVA, photopic, monocular (3, 6, and 9 month visit)
- UCIVA, photopic, binocular (3, 6, and 9 month visit)
- UCNVA, photopic, monocular (3, 6, and 9 month visit)
- UCNVA, photopic, binocular (3, 6, and 9 month visit)
- Defocus curve testing (3, 6, and 9 month visit)
- Anterior Segment Examination

- Pachymetry (6 month exam)
- Auto or Manual Keratometry
- Corneal Topography
- Cycloplegic Refraction (6 month exam)

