### **20.3 ADDITIONAL ENDPOINTS**

The frequency, proportion and 95% confidence intervals of eyes with achieved MRSE within 0.50 D and 1.00 D of intended will be summarized over time. The intended MRSE is defined as “ – Preop MRSE”. The achieved MRSE is defined as “Postop MRSE - Preop MRSE”.

Refractive stability will be evaluated for a consistent cohort (i.e., eyes with data at all periodic study visits). At the point of refractive stability, at least 95% of the eyes in the consistent cohort should have a change  $\leq 1.00$  D of MRSE between refractions performed at 1 month and 3 months after surgery or any two refractions performed at least 3 months apart. The mean change (paired differences) in MRSE between pairs of successive refractions will be calculated. The 95% confidence intervals of the mean changes should include zero.

The depth of focus curve data will be presented graphically and test and control groups will be compared by descriptive analysis. The mean and standard deviation of iDesign aberrometry measurements (HOA) and keratometry (mean and K cylinder) will be reported over time. Manifest cylinder will be analyzed as both non-vector and vector variables (Eydelman, et al, 2006). The frequency and proportion of eyes with

complications and slit-lamp findings, including corneal clarity, will also be reported over time. Other visual acuity endpoints (such as UCDVA, UCIVA, UCNVA and low contrast BSCVA) will also be reported by test versus control group with the mean difference between groups also determined. Results for visual symptoms from the PRVSQ for PRK/LASIK will be analyzed to compare differences between the test and control groups. The frequency and proportion of eyes with reported ocular visual symptoms (non-directed) will be presented. A listing of all serious and/or device-related adverse events will also be provided. Additionally, non-refractive retreatment procedures will be tabulated and summarized.

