**PRSVQ-Lasik Questionnaire** (2015 version) is a self-administered, validated assessment tool designed specifically for those who through correction of refractive error have normal visual acuity, but may still be experiencing problems in vision-related functioning and well-being. The PRSVQ questionnaire is to be administered preoperatively and at designated postoperative study exams.

**Pachymetry** to measure the corneal thickness shall be performed with an ultrasonic pachymeter preoperatively, intra-operatively (as applicable), and postoperatively.

**Photopic Luminance** is defined as 85 cd/m^2 (acceptable range of 80-110 cd/m^2).

**Photopic Pupil Size** is to be performed under photopic room lighting conditions of 480 – 520 lux. Photopic pupil size should be measured using the NeurOptics pupillometer.

**Refractive Stability (preoperative)** is defined as a change of  $\leq 1.00$  D in sphere or cylinder (based on a previous exam, medical records, or prescription) at least 12 months prior to the preoperative manifest refraction. Additionally, the astigmatic axis must also

be within 15 degrees for eyes with >0.50 D of preoperative and historical manifest cylinder.

**Refractive Stability Check for Contact Lens Wearers** is based on a change of not more than 0.50 D in MRS, MRC and as well as keratometric meridians on 2 separate occasions at least 7 days apart with readings following cessation of contact lens wear of 4 weeks for rigid contact lenses (toric or spherical) and 2 weeks for soft contact lenses (toric or spherical).

**Surgical Target** and planning is required prior to the operative exam. All eyes will be targeted for emmetropia. The iDesign 1.3-PRESBY TPS will be used to create a treatment shape for each eye that qualifies for the study. The TPS software used in this study is Version 1.3, which does not require any additional physician adjustments.

**UCVA (Uncorrected Visual Acuity)** shall be measured using the M & S Technologies CTS-1000 Smart System in logMAR format (100% contrast) at a test distance of 4 meters and calibrated to a photopic luminance (80-110 cd/m^2). UCVA testing is to be performed through a +0.25 D trial lens refractive adjustment to compensate for the 4 meter test distance. Detailed instructions for performing UCVA testing are provided in **Appendix G**.

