**PRVSQ-LASIK/PRK**

**This questionnaire asks about your visual symptoms  
OVER THE LAST 7 DAYS.**

**For ALL questions, please mark an  in the box or boxes  
that best describe your answer.**

The next few questions ask about halos.

**Halos** are bright circles or rings that appear around a source of light, such as oncoming car headlights.

Q1a. Over the last 7 days, how often did you experience halos?

- Never (**go to question Q2a**)
- Rarely
- Sometimes
- Often
- Always

If you experienced halos in the last 7 days, please answer the following questions.

Q1b. Did you experience halos... **Check all that apply.**

- When **not** wearing corrective glasses or contacts
- When wearing corrective glasses or contacts
- When wearing any type of sunglasses

Q1c. Did you experience halos... **Check all that apply.**

- During the day
- During the night
- During dawn or dusk

Q1d. Did you experience halos... **Check all that apply.**

- When driving during the day
- When driving at night
- When driving at dawn or dusk

Q1e. Overall, how much were you bothered by halos?

- Not at all bothered
- Slightly bothered
- Moderately bothered
- Very bothered
- Extremely bothered

Q1f. Is there anything you have a lot of difficulty with, or do not do, because of halos?

- No
- Yes. If Yes, please describe:

The next few questions ask about glare.

**Glare** is reflected light making it difficult to see. **Glare** may occur as light reflecting off of water, a window or pavement.

Q2a. Over the last 7 days, how often did you experience glare?

- Never (**go to question Q3a**)
- Rarely
- Sometimes
- Often
- Always

If you experienced glare in the last 7 days, please answer the following questions.

Q2b. Did you experience glare... ***Check all that apply.***

- When **not** wearing corrective glasses or contacts
- When wearing corrective glasses or contacts
- When wearing any type of sunglasses

Q2c. Did you experience glare... ***Check all that apply.***

- During the day
- During the night
- During dawn or dusk

Q2d. Did you experience glare... ***Check all that apply.***

- When driving during the day
- When driving at night
- When driving at dawn or dusk

Q2e. Overall, how much were you bothered by glare?

- Not at all bothered
- Slightly bothered
- Moderately bothered
- Very bothered
- Extremely bothered

Q2f. Is there anything you have a lot of difficulty with, or do not do, because of glare?

- No
- Yes. If Yes, please describe:

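### The plan compares PRVSQ answers between test and control, but these are two eyes of one person and the documented form names no eye

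*SAP*

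**What the plan says.** Both documents commit to a comparison by treatment. Protocol 20.3: "Results for visual symptoms from the PRVSQ for PRK/LASIK will be analyzed to compare differences between the test and control groups". SAP 3.6 takes this down to item level: "responses to each item from the PRVSQ for PRK/LASIK will be analyzed to compare differences between the test and control groups". The PRVSQ row of SAP Appendix I is marked for both Test and Control and describes counts and percentages by level of severity.

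The two groups are fellow eyes. Protocol Synopsis, Study Population Characteristics: "The control eye will receive the iDesign CustomVue treatment, test eye will receive the PresbyT-LASIK". Protocol Section 4: "The dominant eye will be treated with the control product; the non-dominant eye will be treated with test product". Section 4 also requires both eyes of every subject to be treated.

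Protocol Appendix C says that the questionnaire "is a self-administered, validated assessment tool". The form in Appendix O, headed as an example, addresses the subject throughout, for instance "If you experienced halos in the last 7 days, please answer the following questions" and "Overall, how much were you bothered by halos". Appendix A schedules it preoperatively and at 1, 3, 6 and 9 months.

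**The concern.** A questionnaire answered by a person who has one test eye and one control eye yields one answer belonging to both treatments. Unless the answer is tied to an eye, no test group and control group of responses exist to compare. The analysis population (Protocol 20.1, SAP 2.1) is counted in eyes, so a person-level answer has no natural row in the analysis.

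The subject matter makes this more than a drafting slip. Protocol Section 17 says that glare, ghost images, starbursts and halos may be worse than after the control treatment, because the presbyopic ablation brings more spherical aberration. The PRVSQ is the only structured questionnaire on such symptoms in the study. An empty table, or one showing no difference by construction, could be read as reassurance on a risk that the sponsor has itself identified.

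**Working it through.** The plan gives no numerical target for the PRVSQ. Its one sample-size figure concerns intermediate acuity and does not enter here. The check is a reading of the form against the analysis, with some counting.

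1. **Items on the form (Appendix O).** Six symptoms (halos, glare, starbursts, light sensitivity, multiple or double vision, fluctuating vision), each with items a to f, plus Q7: 6 × 6 + 1 = 37.

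2. **What the items record.** Item a is frequency; b, c and d are correction worn, time of day and driving; e is bother; f is difficulty or avoidance. Q7 asks about other symptoms. There is no right/left or test/control field and no instruction to complete the form separately for each eye. Items that can be split by eye: 0 of 37.

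3. **Rules elsewhere.** Appendix A, its notes on the order of testing, and Appendix C describe neither by-eye administration nor a way of attributing an answer to an eye.

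4. **What the comparison would produce.** Take 34 bilaterally treated subjects with complete forms at a visit. That gives 34 records, each from a person with one eye in each group. Suppose k subjects give a particular response.
   - Assigning each record to one group only: no documented basis.
   - Entering each record under both: k/34 − k/34 = 0 for every response and every k, whatever the true symptom burden.

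   A subject left with one treated eye, because surgery on the fellow eye was deferred under Protocol 10.5, would be an exception to the design and would not supply a comparison group.

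5. **Form against table shell.** SAP Appendix I refers to severity; the printed form rates frequency and bother and has no item labelled severity. Either the shell is loosely worded or it was written for another version.

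6. **Skip pattern.** Answering Never to item a skips items b to f of that symptom: 5 × 6 = 30 of 37 items (81%). Even a per-subject table needs a stated denominator for those items: all respondents, or only those reporting the symptom.

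7. **Contrast within the documents.** The SAP calls the non-directed symptoms monocular and counts eyes for slit-lamp findings and complications. For the PRVSQ it counts only responses.

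**The case against.** Three features of the documents point towards by-eye data.

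- Protocol 10.6 introduces the periodic visit list with "The following data shall be assessed and recorded for both eyes during the periodic examinations", and the PRVSQ is on that list. But the same lead-in covers medical history, medications and binocular acuities, so it is generic and creates no by-eye questionnaire.
- SAP Appendix I marks the PRVSQ row for Test and Control. Demographics carries both marks too, although that row is labelled as covering subjects only and the PRVSQ row is not. The marks may therefore signal by-eye intent. They do not say how an answer would reach an eye.
- Appendix O is only an example, the electronic case report forms are not in the documents, and the severity wording in the SAP fits no printed item. This objection has the most force: the fielded form may differ.

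Because of the third point, a reader who infers that the trial cannot deliver a between-eye PRVSQ comparison at all goes further than the documents allow. What they support is that the comparison cannot be produced from the form they contain. Nor should a reader infer that the sponsor intends to enter each answer twice; no passage plans that, and the zero difference is only what would follow.

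It is also fair to say that this is a feasibility study, that the endpoint carries no success criterion, and that the mismatch would probably surface when the tables are programmed. That limits the severity but does not supply the missing link.

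**Conclusion.** The point holds for the form as documented: 0 of 37 items can be attributed to an eye, so the comparison in Protocol 20.3 and SAP 3.6 cannot be produced from it. The conclusion rests on Appendix O representing the fielded form, which the documents suggest but do not establish. The SAP's severity wording is a reason for some doubt and needs reconciling in any case.

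A reader might infer damage to the trial's main conclusions. The documents do not support that: the primary (DCIVA), secondary (DCNVA) and BSCVA analyses do not use the PRVSQ. Nor would by-eye symptom information be lost altogether. The SAP plans non-directed monocular symptoms, and adverse events are counted by eye, with severe glare or halos at 3 months or later among the anticipated events in Protocol 11.1. What is lost is the planned between-eye comparison on the only structured symptom questionnaire. It should be fixed, and cheaply, before analysis.

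**What to change.** In Protocol 20.3, SAP 3.6 and the PRVSQ row of SAP Appendix I, delete the test-versus-control comparison and write, in substance:

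> PRVSQ responses will be reported once per subject, as n and % per item at each scheduled visit. For items b to f, which are skipped after an answer of Never, the denominator will be stated. Results describe the combined two-eye correction and are not attributed to the test or control eye.

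Also:

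- Reconcile the severity wording in SAP Appendix I with the frequency and bother items on the form.
- If the sponsor holds a by-eye version, name it, include it, and analyse it as paired eyes. The rank-sum default for ordinal data in Protocol 20.4 treats the two eyes of one person as independent samples.
- Base by-eye symptom statements on the non-directed monocular symptoms and by-eye adverse events already planned. The open question in Protocol 6.3 names no eye, so confirm that the affected eye is recorded with each response. If it is not, capturing it would be additional data collection under Protocol Section 12.
- A within-subject change from the preoperative visit is optional. It should follow the instrument's own scoring rules, which are not in the documents, and would be an uncontrolled change mixing both eyes' surgery.

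**Cost.** Wording in three places and a stated denominator, with no new PRVSQ data. The protocol change needs Health Canada and IRB approval under Section 12. The between-eye PRVSQ claim is given up unless a by-eye version exists. Adding an eye field to the present form instead would be additional data collection and would depart from an instrument that the protocol describes as validated.
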